4.2 Drug/Device Handling: N/A

4.3 Biosafety: N/A

4.4 Stem Cells: N/A

5.0 Procedures Involved

5.1 Study Design: The study design is cross-sectional. 150 target children (10- to 15-year-olds) will be randomly assigned to one of three conditions: (1) no social support (standard MRI scanning condition); (2) presence of a parent; or (3) presence of a close friend. Outcome measures will be compared across the three social buffering conditions. Pubertal stage will be included as a continuous variable in analyses of physiological and/or brain responses.

Two tasks will be used during the MRI scanning. Both have been shown to activate stress-related regions of the brain in past studies and have been used by our labs. The order of these two tasks will be counterbalanced.

Based on the results of piloting social buffering will EITHER be done with the presence of a buffer in person, or, displayed on screen via a live Zoom feed. All conditions will use the same modality.

Study Overview:

Visit 1: Parent and child will participate in an online video session (via Zoom) lasting approximately 2 hours. Following a detailed overview of study and consent/assent procedures, participants will be asked to complete the following measures:

Parent:

- Questionnaire regarding family income, education level, and family composition
- Parent-report questionnaire about child's general health, behavior, and development (MacArthur Health Behavior Questionnaire; HBQ)
- Parent-report MRI safety screening questionnaire about the child to rule out any contraindications for MRI scanning
- *[If the child is randomized to the parent-present buffering condition],* self-report MRI safety screening questionnaire to rule out any contraindications for sitting in the MRI area

PROTOCOL TITLE: An MRI Study of Learning and Social Support

VERSION DATE: v.10 2024.12.18

- Child life challenges question

Children/adolescents:

- Questionnaire about general health, behavior, and development (MacArthur Health Behavior Questionnaire; HBQ)
- Questionnaire about their relationships with their parents and their best friend (Network of Relationships Questionnaire)
- Questionnaire about anxiety in different contexts (State-Trait Anxiety Inventory for Children)
- Pubertal development questionnaire (Morris and Udry, 1980)
- Safety screening questionnaire to confirm safety in the MRI scanner
- Perceived stress questionnaire
- Child life challenges questionnaire

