Visit 2: Parent and child [*and sometimes, child's close friend*] will come to the Center for Magnetic Resonance Research for a session lasting approximately 2 hours. Note that if buffering occurs in person, we will invite the close friend to attend in person, and if buffering occurs on-line, we will invite them to attend via zoom. Following a session overview and consent/assent procedures, participants will be asked to complete the following measures:

Parent:

- Required safety screening questionnaire to confirm child's safety in the MRI scanner
- [*If the child is randomized to the parent-present buffering condition*], self-report MRI safety screening questionnaire to rule out any contraindications for sitting in the MRI area
- [*If the child is randomized to the parent-present buffering condition*], sit next to scanner bed and listen to music, radio, audio book, podcast, etc. or read a book for duration of MRI scan (approx. 1 hour) OR sit in a separate room while connected via video conference call to research staff in the MRI console room for duration of MRI scan, chatting with the child periodically.

Child:

- Required safety screening questionnaire to confirm child's safety in the MRI scanner
- Saliva sampling at up to 10 time points throughout the testing session to assess levels of stress-sensitive compounds, including cortisol, alpha amylase.
- Children chew on an absorbent sponge for 1-2 minutes to acquire each saliva sample.

- Practice in a pretend MRI machine to gain familiarity with the scanning environment and assess comfort in the scanner bore (i.e., rule out claustrophobia)
- Standard non-invasive structural and functional MRI scanning for 1 hour at 3-Tesla (clinical standard) field strength.
- Collection of physiological data during the MRI scan (respiration belt, pulse oximeter and/or 3 EKG leads, MRI-safe skin conductance electrodes on the fingers or palm of one hand or foot).
- Performance of two tasks during MRI scanning: one emotional faces matching task and one emotionally charged go-no go task.
- Completion of a post-scan survey to assess perceived stress at various points throughout the session.
- Optional: Wearing of an actigraphy device on the wrist for several days to record activity and sleep patterns.

Child's Friend: [Applicable only if the child is randomized to the friend-present buffering condition]

- MRI safety screening questionnaire to rule out any contraindications for sitting in the MRI area

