- Completion of the Network of Relationships questionnaire
- Sit next to scanner bed and listen to music, radio, audio book, podcast, etc. or read a book for duration of MRI scan (approx. 1 hour) OR join the session online via video conference call to research staff in the MRI console room for duration of MRI scan , chatting with the first child periodically.
- *Note: Friend's parent will complete a full consent procedure over the telephone or video conference call prior to the session and will return a signed consent and child safety-screening form via REDCap or by mail or with the participating family.*

5.2 Study Procedures:

Social Buffering Manipulations: Will include 3 between-subjects conditions and both sexes. Participants will be randomly assigned to No Social Partner, Parent, or Close Friend conditions. Definition of Close Friend. We will ask the parent to have the child select the close same-sex friend they want to have accompany them. The parent then has to contact that child's family and get their permission for us to contact them. We have successfully conducted studies in which the child brings their best friend.

Affective Paradigms: Aversive Learning Paradigms: Consent, assent, and questionnaires will occur during an online session (to reduce in-person requirements; minimize the impact of COVID on study feasibility.) At the session, after a reminder of procedures, youth will be separated from their parents. Youth will be taken to a private changing room to change into

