8.0 Study Population

8.1 Inclusion Criteria: Healthy 10- to 15-year-olds. Additional inclusion criteria ensure that youth will be able to follow the study procedures (have sufficient vision, hearing, and language skills to provide verbal and written assent, see and read stimuli presented on the computer screen, and hear verbal instructions provided by the experimenter and/or judges).

8.2 Exclusion Criteria for child participation: Premature birth (less than 37 weeks), congenital and/or chromosomal disorders (e.g. cerebral palsy, FAS, mental retardation, Turner Syndrome, Down Syndrome, Fragile X), Autism Spectrum Disorders, history of serious medical illness (e.g., cancer, organ

transplant), youth using systemic glucocorticoids or beta-adrenergic medications, diagnosed psychiatric illness or psychotropic medication, seizure disorder or other neurological disorder, academic delay or individualized education plan (IEP), contraindications for MRI (implanted medical device; presence of non-removal metal in or on the body, including piercings, orthodontic braces or certain permanent retainers), known pregnancy, tattoo, or history of significant claustrophobia.

8.3 Screening: Screening will occur by asking parents questions at the time of telephone recruitment. To reduce confounding of age and pubertal stage, we will use a stratified recruitment method. During recruitment, parents will be asked 3 questions about their child's physical development, and children will be initially categorized into Pre/Early and Mid/Late Puberty. As cells fill, participants will no longer be enrolled into those cells. Also, to increase minority representation we will sample across zip codes with higher racial and ethnic minority representation.

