10.0 Local Number of Participants

10.1 Local Number of Participants to be Consented: We plan to analyze data from at least 150 target participants. Of these, 50 will bring friends as social buffers. Thus, we plan to enroll at least 200 children. To account for attrition between sessions/replacement for incomplete data, up to 300 children may be consented/enrolled.

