condition was replicated 2000 times and we calculated empirical power, which we defined as the proportion of times out of 2000 where we rejected the null hypothesis at $\alpha = .05$. Given the exploratory nature of this analysis and to simplify the simulation for the power analysis, we omitted covariates and did not vary the effects for the other condition contrasts (i.e., they were always fixed to 0). Next, we fit a path model using the lavaan package in R.

Our findings suggest that in order to detect mediation, the effect of condition on the mediator must be large and the effect of the mediator on the outcome must be medium or large. In addition, if the effect of condition on the outcome is not large, but small or medium sized, then we will be underpowered and would likely conclude complete mediation, when mediation may only be partial or non-existent. Based on this power analysis, it is likely that the MDES for the moderated mediation models will need to be at least medium to large as well.

Missing data. Because we will replace participants who do not come in for session 2 after doing session 1 (which is rare in our experience), we should have 150 completed participants. Missing data, however, could arise from problems in obtaining good imaging data. Participants also often fail to fully complete questionnaires and/or refuse to provide information on household income. If there is missingness in any of the dependent or independent variables, multiple imputation will be used (Little & Rubin, 2014; Peng, Harwell, Liou, & Ehman, 2006; Schafer & Graham, 2002). Variables related to the missingness and the variables missing data will be included in the missing data model. In the event that missingness is not at random (MNAR), we will investigate the use of models for non-ignorable missing data.

- 15.4 Data Integrity: Biospecimen data will be assayed in labs that have standard quality control procedures. MRI data reviewed for raw data quality and artifact detection.

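### The friend is secured only after assignment and session 2 non-attenders are replaced, so selective loss from the friend arm is possible and the plan neither prevents nor reports it

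*Combined protocol and SAP*

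**What the plan says.** The protocol does not state when randomisation takes place, but its conditional wording points to an order. In section 5.1, the parent's own MRI-area screen is listed already at Visit 1, to be done "If the child is randomized to the parent-present buffering condition". The friend's procedures at Visit 2 are headed "Applicable only if the child is randomized to the friend-present buffering condition".

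Section 5.2 describes random assignment and then how the friend is found: the child picks a same-sex close friend, and the parent must approach that family "and get their permission for us to contact them". The friend's parent "will complete a full consent procedure over the telephone or video conference call prior to the session" (section 5.1), and section 11.1 describes the same consent and screening route.

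The inclusion criteria in section 8.1 start from "Healthy 10- to 15-year-olds" and add only the abilities needed to follow the procedures. Neither they, nor the exclusions in 8.2, nor the telephone screening in 8.3 mention an available friend.

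On losses, the Missing data paragraph of section 15.3 says "we will replace participants who do not come in for session 2 after doing session 1", calls this rare, and expects 150 completed participants. Section 10.1 adds: "To account for attrition between sessions/replacement for incomplete data, up to 300 children may be consented/enrolled". No rule covers a friend who cannot be found, declines or fails screening. No as-randomised analysis is stated, and no reporting of losses by arm.

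**The concern.** Randomisation makes the arms comparable at assignment. That comparability is kept only if what happens afterwards does not remove different kinds of children from different arms. Here one arm has a hurdle that the control arm lacks: a second family has to cooperate. Whether a child can produce a willing close friend is plausibly related to peer acceptance, anxiety and response to threat.

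If such children miss session 2 and are replaced by children who clear the hurdle, the friend arm is filled with children who have an available friend, while the other arms keep both kinds. The friend-versus-no-partner and friend-versus-parent contrasts would then mix the effect of the friend's presence with the difference between these children. Hypothesis 2 in section 2.3 depends on the friend arm, so a main question of the study is exposed.

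**Working it through.** **The plan's own numbers.** 150 target children in three arms gives 150/3 = 50 per arm, if allocation is equal. 150 + 50 friends = 200, the enrolment figure in section 10.1. These agree and are not in dispute.

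**Order of events.** Set side by side, sections 5.1, 5.2 and 11.1 give: arm known by Visit 1; friend chosen and contacted for friend-arm children; friend's parent consents and the friend is screened before or at Visit 2; session 2 non-attenders replaced. This order is inferred from the conditional text.

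**Size.** The documents give neither of the two quantities needed, so both are assumptions:
- q, the share of children assigned to the friend arm who are lost for want of a friend;
- D, the outcome difference, in SD, between children without and with an available friend.

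Suppose the friend's presence has no effect. The control mean is a mixture, shifted by qD from the mean of children with a friend; the friend-arm completers are not shifted. So:
- bias = q × D in absolute value;
- SE = sqrt(1/50 + (1 + q(1−q)D²)/50), close to sqrt(2/50) = 0.20 SD;
- type I error of an unadjusted two-sided test = P(|Z + bias/SE| > 1.96);
- number randomised to the friend arm to obtain 50 = 50/(1−q), rounded up.

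| q | Bias in SD at D = 0.3 / 0.5 / 0.8 | Type I error, % | Randomised for 50 |
|---|---|---|---|
| 2% | 0.006 / 0.010 / 0.016 | 5.0 / 5.0 / 5.1 | 52 |
| 10% | 0.03 / 0.05 / 0.08 | 5.3 / 5.7 / 6.8 | 56 |
| 20% | 0.06 / 0.10 / 0.16 | 6.0 / 7.9 / 12.2 | 63 |

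Worked case, q = 20% and D = 0.5: bias = 0.2 × 0.5 = 0.10. SE = sqrt(0.0200 + 1.04/50) = sqrt(0.0408) = 0.202. Ratio = 0.10/0.202 = 0.495. Type I error = P(Z > 1.465) + P(Z < −2.455) = 0.0715 + 0.0070 = 0.0785, about 8%.

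**Under Tukey.** Section 15.3 uses Tukey's HSD for pairwise comparisons. With three groups and 150 − 3 = 147 degrees of freedom, the critical value on the z scale is about 2.37, so the nominal per-pair rate is about 1.8%. In the worked case it becomes P(Z > 1.87) + P(Z < −2.86) = 0.031 + 0.002, about 3%. The bias itself stays at 0.10 SD whatever the critical value.

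**For scale.** At 50 per arm an unadjusted comparison detects (1.96 + 0.84) × 0.20 = 0.56 SD with 80% power.

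**The case against.** The strongest reply is that nothing shows this loss will happen. The plan calls session 2 non-attendance rare. Section 5.2 reports earlier studies in which children brought a best friend, and section 11.1 says the same recruitment route is in successful use. Buffering may be by Zoom, which eases attendance. This stands: the size may be negligible. But the statement on rarity carries no rate and is not given by arm, earlier success does not say how many children could not bring a friend, and Zoom still needs a willing friend and a consenting family.

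Second, section 5.2 plans to compare relationship quality, the peer scales and the symptom scales across arms and to adjust if they differ. That is aimed at the right confounder and is a real partial safeguard. It does not close the gap: for relationship quality it acts only on significant differences, section 15.1 adds a requirement of association with the outcome, tests at about 50 per arm can miss an imbalance that matters, and only measured traits are covered.

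Third, the type I figures are for a simple two-arm test. The plan begins with a three-way interaction and adds Tukey and Benjamini-Hochberg corrections, so actual rates would differ. A constant mean shift also need not bias the interactions with puberty. Both points stand.

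Three stronger readings are tempting, and the documents do not support them:
- A reader might infer that friendless children are dropped and the arms are in fact not comparable. No text says so; there is simply no rule for that case.
- A reader might take the ceiling of 300 against 200 as a sign of expected friend-arm loss. It is an upper limit that covers all attrition and incomplete data, so it says nothing about one arm.
- A reader might extend the point to parents. A parent takes part in both visits in every arm, so only a parent who fails the MRI-area screen for in-person buffering would matter.

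**Conclusion.** The concern holds as a risk of unknown size. As written, the plan allows selection after randomisation that depends on having an available friend and acts on the friend arm alone. It has no rule for an unavailable friend, and it would not show the loss if it occurred. If the loss is as rare as the plan expects (2% taken as an example), the bias is at most about 0.016 SD for differences up to 0.8 SD and can be ignored. At an assumed 20% loss and 0.5 SD difference it is 0.10 SD, half of a pairwise standard error. That would not overturn a large effect but could colour a modest one. The conclusion rests on the inferred order of assignment and friend recruitment, and on assumed values of q and D.

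**What to change.** 1. At telephone screening, before assignment, ask every family in all arms to identify a same-sex close friend whose family is willing to be contacted. Randomise, or reveal the arm, only afterwards. If buffering is in person, complete the parent's MRI-area screen for all arms before assignment as well.
2. State what happens to a child in the friend arm whose friend then declines, is unavailable or fails screening.
3. Recruitment may continue to 150 completers, but add an as-randomised analysis that keeps every randomised child (apart from those whose data section 12 requires to be excluded or destroyed). Use the Visit 1 health and behaviour, relationship and anxiety data in the multiple imputation already planned. This assumes that losses are explained by the Visit 1 data.
4. Report losses and replacements between assignment and Visit 2 by arm and reason.

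Cost: a few screening questions and some SAP wording; the target of 150 is unchanged. Children with no identifiable friend would not be enrolled, which narrows the population slightly. A named friend may still decline, so some loss can remain, and items 3 and 4 are there for that. If enrolment is too far advanced for item 1, they can still be done where the records were kept. This is a cheap improvement.

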16.0 Confidentiality

Data Security: Only authorized research staff will have access to the data, and all data will be stored in REDcap databases, secure servers (CMRR and Minnesota Supercomputing Institute) or in locked file cabinets. Names and contact information, and child birth date will be maintained in REDcap database to avoid enrolling participants more than once, to calculate age at test, and to allow us to contact families who have participated with overall study findings. IRB and CMRR policies require that we maintain the MRI safety screening information for the same duration that we maintain

consent documents. These will be stored in locked file cabinets and/or uploaded to a secure REDcap database.

A password-protected document linking name and ID number will be kept on REDCap until the conclusion of the study in case we must contact a family for any reason, including identification of an incidental MRI finding. This document will be destroyed at the conclusion of the study.

All data files are de-identified, password protected, or maintained in secure storage locations (REDcap and/or University Box). All paper copies are stored in locked cabinets, and will be digitized/verified/destroyed.

16.1 No documents will be placed in participants' medical, employment, or educational records.

17.0 Provisions to Monitor the Data to Ensure the Safety of Participants

17.1 Data Integrity Monitoring:

All of the planned procedures meet the NIH definition of minimal risk. The PI and Study Coordinator will meet regularly to ensure that all study protocols are followed and best practices are applied. The Study Coordinator will bring any identified protocol violations to the PI in a timely fashion and team members will be retrained, if needed.

17.2 Data Safety Monitoring:

This project is considered a clinical trial because it involves a) random assignment to condition, and b) physiology or brain activity is being measured.

There is no risk associated with the assignment to conditions (No Social Buffer, Close Friend, Parent). All conditions resemble naturally occurring social situations that children might experience, and there is no inherent danger to one condition over another as there would be for, say, a drug vs placebo trial.

Further, in two of the conditions, the presence of another person is expected to provide a social buffer whose stress reduction potency by condition is what is being tested. All target youth experience the same stressor.

The other potential risks of this study to which all of the participants are exposed regardless of condition are low, including, claustrophobia or fear of the MRI tunnel, loud noises in the scanner, and risk of choking during saliva collection.

The steps taken to Reduce or prevent these risks include: use of proper saliva collection materials, and by completing thorough safety screening prior to MRI scanning, and providing youth with a simulated MRI experience

first. These risks are all managed by the routine processes monitored by our IRB and the CMRR Safety Committee. Adverse Events (Aes), including Serious Adverse Events (SAEs) such as deaths, hospitalizations, and life-threatening events and Unanticipated Problems (Ups), will be managed and reported, as required, to the IRB and relevant monitoring authorities. All members of the project have received human subjects training and certification in FDA Good Clinical Practice through the Collaborative Institutional Training Initiative (CITI) curriculum.

The following information will be collected to monitor risk:

- The number of youth refusing the MRI scan.
- Any instance of gagging during the saliva collection.

How often will risks be assessed? Every three months we will examine the number of youth refusing the MRI scan and adjust procedures, if needed, to improve participant tolerance. In our experience, few youth of this age who have agreed to come in for testing end up refusing the MRI scan once they are here.

The individuals responsible for trial monitoring and advising the appointing entity. Because of the low level of risk in this study, the PI, [name] will be responsible for monitoring and reporting events for this project.

18.0 Provisions to Protect the Privacy Interests of Participants

18.1 Protecting Privacy: Once the participant has been tested, identifying information will be removed, and all materials will be identified with a participant number only. A master list with participant names, addresses and contact information will be maintained in secure REDcap database, separately from the data and study materials. A master list connecting links from study ID to participant name will be maintained in a password-protected spreadsheet on RedCap and/or University Box Storage. Only researchers involved in the study and having a legitimate reason for connecting data to an individual participant (e.g., in the event of a clinically-relevant incidental MRI finding) will have access to the file that merges participant number and personal information. Non-data study materials (e.g., consent forms, payment forms, MRI safety screening forms) will be maintained in a secure REDcap database separately from the de-identified data.

Considerable efforts are made to make participants comfortable, despite the nature of the stressor in the second visit. Consent and all study

procedures will be conducted in private rooms. During consent/assent multiple efforts are made to make it clear that participation is optional and that the child is in control of refusal; for example, payment is given at the start of the session rather than upon completion. Collection of biological measures, placement of electrodes, and administration of sensitive questionnaires are all done with a “matter of fact” attitude to minimize any feeling of embarrassment. Should a participant need to skip a portion or end a session early, experimenters are trained to accept this as a standard procedure when working with children rather than a problematic ending to the session. We have successfully guided hundreds of youth through these very procedures without undue problem, including longitudinal studies where the participants continue to return.

Female participants who have begun menstruation will be verbally screened for possible pregnancy. If a child thinks she could be pregnant, we will not scan her. By Minnesota Statute, we are not allowed to break confidentiality to inform parents of a teen pregnancy. If a child tells us that she might be pregnant, we will offer her a urine pregnancy test to give her more information but will not require anyone to take a pregnancy test. If the test is positive, we will encourage her to tell her parents, and will offer to sit with the child while she informs a parent. If a child thinks she may be pregnant or has a positive pregnancy test, we will provide her with information on services that she can access to receive pre-natal care and counseling.

18.2 Access to Participants: This study does not involve access to participant medical records or other private records. Any personal information collected in this study will be provided directly by the participants.

